Nine adults (53.1 ± 10.7 years, BMI $37.4 \pm 9.9 \text{ kg/m}^2$) with diabetes used the *NEAT!* app on 21.9 ± 8.0 days/month. *NEAT!* interrupted continuous bouts (≥ 20 minutes) of sitting by providing prompts on the smartphone to engage in light-intensity activity for ≥ 2 minutes. Prompts to interrupt sedentary time were given 5.8 ± 3.5 times/day. Participants reduced their sedentary time by $8.1 \pm 4.5\%$ (156.4 ± 75.0 min/day) between baseline and 1 month.¹⁴ Nearly 88% of participants indicated they would use *NEAT!* again in the future, suggesting high acceptability of the first iteration of the technology.

To inform the development of our *NEAT!*2 sedentary reduction intervention and update the *NEAT!* smartphone application, we surveyed 42 participants (61.8 ± 7.6 years, 67% female) on their beliefs about sedentary behavior and preferences for participating in a sedentary behavior reduction program. Nearly 80% of participants were located within the Columbia, SC region. Additionally, 88% of participants own a smartphone and 80% indicated they would be interested in participating in a sedentary reduction program.

D. RESEARCH DESIGN AND METHODS AND DATA ANALYSIS

Design Overview: This study is a three-group randomized controlled trial comparing changes in sedentary behavior between the *NEAT!*2 intervention with or without coaching calls and a control group in adults with past or present knee symptoms, injuries, or surgeries. A total of 90 participants will be randomized into one of three groups 1) *NEAT!*2 2) Delayed *NEAT!*2 or 3) *NEAT!*2+Calls. Data will be collected at baseline and months 1, 3, and 6.

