- 1) **NEAT!2:** *NEAT!2* is guided by the Dual-Process Theory¹⁶ and targets both automatic and controlled processes.¹⁷ Participants randomized to *NEAT!2* will have their *NEAT!2* app turned on after randomization. Using the smartphone's internal accelerometers, *NEAT!2* detects periods of movement vs. non-movement. When 30 minutes of continuous non-movement or sedentary time is detected, the *NEAT!2* app will initiate a reminder notification via vibration or audio as well as display a reminder on the phone's lock/home screen. This novel approach will take advantage of the frequent number of times an individual looks at his/her phone.¹⁸ If and when the app detects activity/movement, the 30-minute timer will restart; thus, the app will only provide notifications when prolonged bouts of inactivity are objectively detected. Further, the app will only trigger notifications during participants waking hours. Each notification will consist of a different message. Participants will be asked to use the app for the 3 months of the intervention. Participants will be given an initial goal to reduce total sedentary time by 30 minutes/day, ultimately progressing to a 90 minute/day reduction by 3 months. After the 3-month assessment, participants randomized to *NEAT!2* will have the option to continue using the app until 6 months.
- 2) **Delayed NEAT!2:** Participants randomized to the delayed control condition will not receive any contact or app between baseline and 3 months. However, after completing the 3-month assessment, participants in the delayed condition will receive the *NEAT!2* application. Participants will then have the option to use the app between 3 and 6 months.

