- Waist Circumference will also be assessed as a predictor of abdominal visceral fat. Measurement will be done twice during expiration, taking the average for analyses, by positioning an anthropometric tape midway between the palpated iliac crest and the palpated lowest rib margin in the mid-axillary lines (smallest part of the waist).

Evaluation: Following completion of the 3 or 6 month assessment, participants will be asked to complete a short evaluation form asking about their feelings and attitudes regarding the NEAT!2 program and the NEAT!2 application. The evaluation will aid in future research utilizing the *NEAT!2* application or research directed at reducing sedentary behavior in this population.

Statistical Analysis: Baseline participant characteristics will be described. Mixed ANCOVA's will be conducted to examine differences in sedentary behavior, physical function, and patient-reported outcomes across time by group. Additionally, we will control all sedentary time analyses for moderate intensity physical activity. All analyses will be performed using SAS 9.2 and SPSS.

E. PROTECTION OF HUMAN SUBJECTS

1. TARGET POPULATION:

We will aim to recruit 90 participants from Columbia, SC and surrounding areas. The target population will consist of adults over the age of 40 who identify with past or present knee pain, injury, or surgery.

Inclusion criteria: Eligible participants will 1) be at least 40 years of age, 2) own an Android or iOS smartphone, 3) have their smartphone near them (in their pocket, in their hand, or within 10 feet of them for >50% of their waking day) 4) be willing to download the study application on their smartphone and have the application be compatible with their device, 5) spend at least 7 hours/day sitting, assessed by the SIT-Q, 6) have at least 4 days of valid accelerometer data at baseline, 7) have knee pain (at least one knee with pain, aching, or stiffness on most days for one month of the last 12 months), knee injury, or knee replacement within the last 5 years, and 8) read, speak, and understand English.

Exclusion criteria: Participants will only be excluded if they 1) have any contraindications to activity, 2) have a mobility limiting comorbidity (e.g. spinal stenosis), or 3) have a scheduled surgery (i.e., total knee replacement) within the next 6 months.

2. RECRUITMENT PLANS:

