We will target recruitment channels including: 1) promotions in publications with low or no advertising cost (i.e., Craig's List); 2) electronic and social media recruitment blurbs (i.e., Facebook, Twitter, website, email newsletter, electronic billboard, etc.); 3) posting flyers around USC campus area and local Columbia businesses, health centers, rehabilitation or orthopedic centers; 4) word of mouth; and 5) emails to individuals from previous studies who expressed interest in participating in future trials.

All recruitment material will list study eligibility criteria and requirements and include a phone number, email address, and website where participants can reach staff if they have any general questions regarding study participation.

3. EXISTING DATA/SAMPLES:

Not applicable

4. CONSENT/ASSENT:

Written informed consent will be obtained in person. Full disclosure will be made of the nature and potential risks of participating in the study. Prior to starting, all participants will be asked if they have any questions about their participation to ensure they understand the procedures. The consent form has been developed according to the requirements of the University of South Carolina Institutional Review Board. All participants will receive a copy of their signed consent form. A copy of all signed IRB-approved consent forms will be kept in a locked file.

5. POTENTIAL RISKS:

Risks associated with interrupting sedentary time with brief bouts of light-intensity physical activity such as standing or light ambulation are minimal. Participants may experience skin irritation from wearing the activPAL accelerometer for 7 days at each assessment. In the event the participant experiences skin irritation, we will ask the participant to remove the device. We will provide them with additional tape, with multiple options available to accommodate individual reactions and preferences to medical grade tape, to reaffix to the other leg.

6. POTENTIAL BENEFITS:

Participants may or may not directly benefit from participating in this study, however the risks of participating in either randomized group are considered minimal. Participants may gain skills and knowledge regarding how to decrease sedentary behavior.

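### The closed exclusion list lets two members of one household enrol and be randomised separately, so a Delayed control could live with an app user; the likely dilution is small and the fix is cheap.

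*Combined protocol and SAP*

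**What the plan says.** **Eligibility (Section E.1, Target Population).** The exclusions are a closed list: "Participants will only be excluded if they 1) have any contraindications to activity", followed by a comorbidity that limits mobility, with planned surgery in the coming 6 months as the third and last item. The eight inclusion criteria begin "Eligible participants will 1) be at least 40 years of age, 2) own an Android or iOS smartphone" and all concern the individual. Neither list mentions the household.

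**Recruitment (Section E.2).** Five channels are listed, in and around one city. They end with "4) word of mouth; and 5) emails to individuals from previous studies who expressed interest in participating in future trials".

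**Allocation (Section D, Design Overview).** "A total of 90 participants will be randomized into one of three groups". The ratio is not stated, and nothing is said about allocating co-residents together.

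**Intervention and control (Section D, Randomized Conditions).** After 30 minutes without movement, the "app will initiate a reminder notification via vibration or audio as well as display a reminder on the phone's lock/home screen". Both app arms have a reduction goal that rises from 30 to 90 min/day, and the Calls arm also discusses educational handouts with a coach. Delayed participants "will not receive any contact or app between baseline and 3 months".

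**The concern.** The Delayed arm is useful in Aims 1 and 2 only if it stays untouched until the 3-month assessment. The eligibility rules give staff no ground to decline an eligible spouse or relative of someone already enrolled, and word of mouth is an obvious way for such a person to arrive. If the two are randomised separately, one may be a control while the other has the app. The control may then notice prompts, learn the sitting goal, read the handouts, or sit less because a partner gets up during a shared meal or television programme. Any such change lowers sitting time in the control arm and pulls the app-versus-control difference toward zero. A household split between NEAT!2 and NEAT!2+Calls could blur that contrast in the same way.

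No other part of the plan guards against this. The equipoise induction is aimed at differential attrition, and the idle test app at technical compatibility. The activity-monitor questionnaire in Table 1 records the participant's own change in monitor use. Marital status is collected, but not whether a partner is in the trial. As planned, contamination within a household would be neither prevented nor visible in the data.

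**Working it through.** The plan has no figure of its own to reproduce: it gives no power, alpha, planning SD, dropout rate or allocation ratio. The sums below only size the gap.

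**Inputs from the protocol**
- 90 participants in three arms (Design Overview).
- A goal of a 90 min/day reduction by 3 months (Randomized Conditions). This is a behavioural goal, not a powered effect.
- SD of change 75 min/day, from a nine-person pilot in diabetes (Section C). It is the only SD of change in sedentary minutes given.

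**Assumptions, not in the protocol**
- 1:1:1 independent allocation, so 30 per arm.
- Households of two participants.
- A share *h* of participants with an enrolled co-resident: 5%, 10% or 20%.
- Spillover *s*, the fraction of the app effect that an exposed control takes on: 10%, 25% or 50%.
- Two-sided alpha of 0.05 for the power figures.

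**Step 1: exposed controls.** The co-resident of a Delayed participant is in an app arm with probability 2/3, so the expected number exposed is 30 × *h* × 2/3.
- *h* = 5%: 30 × 0.05 × 2/3 = 1
- *h* = 10%: 30 × 0.10 × 2/3 = 2
- *h* = 20%: 30 × 0.20 × 2/3 = 4

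Cross-check by household: a pair is split between Delayed and an app arm with probability 2 × (1/3) × (2/3) = 4/9. At *h* = 20% there are 90 × 0.20 / 2 = 9 pairs, and 9 × 4/9 = 4, which agrees.

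**Step 2: dilution of the contrast** = (exposed / 30) × *s*.

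| *h* | Exposed of 30 | *s* = 10% | *s* = 25% | *s* = 50% |
|---|---|---|---|---|
| 5% | 1 | 0.3% | 0.8% | 1.7% |
| 10% | 2 | 0.7% | 1.7% | 3.3% |
| 20% | 4 | 1.3% | 3.3% | 6.7% |

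**Step 3: in minutes.** If the true difference equalled the 90 min/day goal, the loss would run from 90 × 0.0033 = 0.3 to 90 × 0.067 = 6 min/day. The standard error of a difference between two arms is 75 × √(2/30) = 19.4 min/day, so the worst case is 6 / 19.4 = 0.3 standard errors.

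**Step 4: in power.** For a true difference of 60 min/day with 30 per arm, the worst-case dilution of 6.7% lowers power from 87% to 82% at SD 75, and from 64% to 58% at SD 100 (an assumed larger SD). At the low end (0.3%) the change is less than half a percentage point.

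**The case against.** The strongest reply is that the whole size rests on assumptions. Both members of a household would have to meet eight criteria, including at least 7 hours of sitting a day, a qualifying knee history, a compatible phone kept close by, and four valid accelerometer days. Word of mouth is one of five channels and does not imply a shared home. The 20% end would mean 18 of 90 participants in such pairs. Spillover may also be weak: a prompt follows the user's own stillness, not the control's, and its text appears on the user's own screen. All of this stands. It is why the spillover range starts at 10% and the result is called small. It does not close the gap in the criteria.

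A reader might go further in three ways that the documents do not support.

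- **That controls will hear the prompts.** Prompts come by vibration or audio, so they need not be heard, and nothing says that goals or handouts are shown to others. Exposure is possible; the protocol does not show that it occurred, or that any pair enrolled.
- **That correlated pairs make the trial's precision wrong.** No precision is stated. The Statistical Analysis paragraph names a mixed ANCOVA without listing its terms, so how it treats pairs is unknown. For any two-arm contrast under independent equal allocation, a pair falls in the same compared arm with probability 1/9 + 1/9 = 2/9 and is split between the two with probability 2 × 1/9 = 2/9. Positive correlation raises the variance in the first case and lowers it in the second, so the effect cancels in expectation.
- **That power would collapse.** Larger losses need dilution of 10–20%, which lies outside the range derived above.

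It can also be said that the study has stopped, as the note under the title records. That limits which part of the fix can still be used. It does not change the reading of the criteria.

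**Conclusion.** The gap is real but minor. As written, the criteria allow co-residents to enrol and be randomised apart, and the plan neither prevents nor records it. Any spillover would bias the Aim 1 and Aim 2 contrasts against Delayed toward no difference. Within the assumed ranges the shrinkage is about 0.3–7%, small beside the sampling error of a 30-per-arm comparison. The co-residence share, the spillover and the equal allocation are all assumptions. The point is a cheap improvement to a stated rule; it does not call the trial's conclusions into question.

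**What to change.** For a restart or a successor trial, add a fourth exclusion to Section E.1: another member of the household is already enrolled. One question on the online screener is enough to check it.

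The cost is a few recruits. At *h* = 5%, 10% and 20% the numbers turned away are about 2, 4 to 5, and 9 of 90. If the 9 were not replaced, arms would fall to 27 and the standard error would rise by a factor of √(30/27) = 1.05. That is of the same order as the worst-case dilution avoided, so replacements should be recruited.

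For people already enrolled, establish from study records which participants lived together. If any Delayed control lived with an app-arm participant, repeat the Aim 1 and Aim 2 comparisons without the exposed controls and report both results. A household random effect is not advised: on these assumptions there would be only about 2 to 9 pairs, too few to estimate it well.

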- 3) **NEAT!2+Calls:** *NEAT!2+Calls* participants will have their *NEAT!2* app turned on after randomization. In addition, to receiving the identical app and given the same goals as participants randomized to *NEAT!2*, *NEAT!2+Calls* participants will receive bi-weekly coaching calls. Coaching calls will be completed by trained coaches, be semi-scripted, and last approximately 10-15 minutes. During calls, coaches will use motivational interviewing techniques, discuss goal progression and educational handouts, problem solve, and set a SMART (specific, measurable, attainable, realistic/reward, timely) goal related to reducing sedentary time. All calls will be recorded and timed to allow the assessment of treatment fidelity. After the 3-month assessment, participants randomized to *NEAT!2+Calls* will have the option to continue using the app until 6 months. During this time, participants will not receive any coaching calls.

Treatment Fidelity: Telephone sessions will be audiotaped, and a 15% sample rated for treatment fidelity on a quarterly basis. If fidelity falls below 80%, coaches will be retrained. Fidelity checklists will assess intended session content (e.g., app usage, SMART goal setting). [name] will train the coaches on the intervention and will oversee the fidelity evaluation. Coaches will meet with [name] once a month to review treatment delivery.

Assessments: Participants will be asked to complete four in-person assessments at baseline, 1 month, 3 months, and 6 months. All in-person assessments will take place

at the TecHealth Center at the University of South Carolina ([name]) and each session will be last approximately 45 minutes in length. Table 1 provides an overview of what outcomes will be assessed, how they will be assessed, and at what time points.

Table 1. Study Outcomes and Measures				
Concept	Variable	Measure	Data Collection	Time Points
Aim 1 Outcomes				
Sedentary Behavior	Objectively measured sedentary behavior	Sitting minutes/day and Sitting bouts >30 minutes during waking hours	ActivPal worn on thigh for 7 days for 24 hours/day	0, 1, 3, & 6 months
	Daily diary	Times monitor on/off, awake/sleep	Paper log for 7 days	0, 1, 3, & 6 months
Aim 2 Outcomes				
Physical Function	Objectively measured physical function	Timed up and go; 30-second chair stands, 6-minute walk test based on OARSI recommended procedures ¹⁹	In-Person Assessment	0, 1, 3, & 6 months
Demographic, Health Status, and Process Variables				

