Participants who are adherent to the intervention and reduce sedentary time may have greater reductions in pain and improvements in physical function. If the intervention is acceptable, safe, and effective, it may provide an innovative approach to reduce sedentary time among adults with previous or past knee symptoms, injuries, or surgeries.

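### 'Safe' is a condition for the programme's use, but discrete adverse events are not collected systematically, and spontaneous reports in months 0-3 may differ by arm

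*Combined protocol and SAP*

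**What the plan says.** Section E.6 looks ahead to a three-part judgement: "If the intervention is acceptable, safe, and effective, it may provide an innovative approach to reduce sedentary time". Two of the parts have instruments. Acceptability has the evaluation form in section D, and effectiveness has the ActivPAL and the function tests. Safety has no measure of its own.

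The only procedure for a harm is in E.5 (Potential Risks), and it concerns the measuring device: "In the event the participant experiences skin irritation, we will ask the participant to remove the device". It says what to do and does not ask for a record. The paper log in Table 1 holds only monitor on/off and awake/sleep times.

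The analysis covers three groups of outcomes: "Mixed ANCOVA's will be conducted to examine differences in sedentary behavior, physical function, and patient-reported outcomes across time by group".

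The visit schedule is common to all arms: "Participants will be asked to complete four in-person assessments at baseline, 1 month, 3 months, and 6 months". Contact between visits is not. In the coached arm, "participants will receive bi-weekly coaching calls", while the Delayed arm "will not receive any contact or app between baseline and 3 months". For the app-only arm section D describes automated notifications and no staff contact: "Participants will be asked to use the app for the 3 months of the intervention". After month 3 the coached arm loses its extra contact: "During this time, participants will not receive any coaching calls".

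**The concern.** If no one asks about falls, injuries or care sought, a report of no such events cannot be told apart from a failure to ask. The population has knee pain, injury or replacement, and the app arms are asked to progress to 90 minutes a day less sitting, so these are reasonable events to ask about. A later statement that the programme is safe would have no event data behind it.

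The second issue is comparability. Events that surface only when a participant happens to mention them depend on how often that participant speaks to staff. In months 0-3 that frequency is set by the randomised arm. If such mentions were counted, the coached arm could appear to have more harm than the app-only or control arm at the same true risk.

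**Working it through.** The plan states no harm rate or safety sample size, so there is no figure to reproduce. The check is a reading of the documents followed by two illustrations.

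**1. What is and is not collected.** Table 1, the outcome descriptions, the Statistical Analysis paragraph and E.1 to E.9 contain no adverse-event definition, question, log or tabulation. E.1 to E.9 are numbered without a gap, so nothing suggests that a safety section was removed. KOOS, PROMIS (pain intensity, pain interference, mobility) and the three function tests are taken at 0, 1, 3 and 6 months in every arm. KOOS asks about the past week, while visits are one to three months apart, so a flare that resolves between visits can be missed. None of these measures is described as recording falls, injuries, care sought or skin reactions. Under E.9, data collection stops at withdrawal and no reason is requested.

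**2. Scheduled staff contacts after baseline, up to month 3.**
- NEAT!2 and Delayed NEAT!2: visits at months 1 and 3 = 2.
- NEAT!2+Calls: 2 visits + about 6 calls = 8, a ratio of 8/2 = 4. This reads bi-weekly as every two weeks. The term is not defined; twice a week would give about 26 calls and 28 contacts.

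**3. Possible size of unequal reporting (all values of p are assumptions).** Events fall uniformly over weeks 0-13 with the same true risk in each arm. Calls are at weeks 2, 4, ..., 12 and visits at weeks 4.33, 13 and 26. Each contact after the event brings it out with probability p. With k contacts remaining, P(reported) = 1 - (1 - p)^k, averaged over event time.
- Visits only: k = 3 for the first third of the period and 2 for the rest. At p = 0.1: (1/3)(1 - 0.9^3) + (2/3)(1 - 0.9^2) = 0.090 + 0.127 = 0.217.
- Coached: k = 9 (weeks 0-2), 8 (2-4), 7 (4-4.33), 6 (4.33-6), 5 (6-8), 4 (8-10), 3 (10-12), 2 (12-13). Weighting by interval length gives 0.428 at p = 0.1.

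| Chance of mention per contact | Coached arm | Visits only | Ratio |
|---|---|---|---|
| 0.1 | 43% | 22% | 2.0 |
| 0.2 | 67% | 40% | 1.7 |
| 0.5 | 94% | 79% | 1.2 |
| 0.5 per visit, 0.1 per call | 84% | 79% | 1.06 |

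**4. What zero events would show with complete collection.** The one-sided 95% upper bound is 1 - 0.05^(1/n). Allocation is not stated; equal allocation of 90 gives 30 per arm and 60 in the two app arms.
- n = 30: 1 - 0.05^(1/30) = 9.5%.
- n = 60: 1 - 0.05^(1/60) = 4.9%.

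With a true risk of 1%, the chance of seeing at least one event among 60 is 1 - 0.99^60 = 45%.

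**The case against.** The strongest reply is that the word 'safe' appears once, in a conditional sentence, and that no aim, outcome or analysis plans a safety conclusion. E.5 classes the risks of light activity as minimal, and deleting the word would remove the inconsistency. That stands, and it is why deletion is offered as the fallback.

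A reader might infer that the trial has no safety information at all. The documents do not support that. Worsening knee symptoms, the most plausible harm here, are measured on the same schedule in every arm and compared by group. The gap is confined to discrete events.

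A reader might also infer that harms will be reported unequally because the coached arm is asked about them more often. The listed call content is motivational interviewing, goals, handouts and problem solving. No harms question is described, and nothing says that a harm mentioned on a call becomes data. Only the possibility of unequal spontaneous reporting, in months 0-3, can be supported. Stopping the step 3 model at month 3 gives larger ratios, from 2.8 (36% against 13%) to 1.5 (89% against 58%), but this leaves out the month-6 visit that every arm is asked to attend.

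Finally, it is tempting to count the Delayed arm's months 3-6 as app-exposed and quote a zero-event bound of 3.3% for 90 people. Section D makes app use optional in that period, so availability is not exposure.

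**Conclusion.** The point holds in a limited form. The plan names safety as a condition for use but does not systematically collect falls, new knee injuries, care sought for the knee or skin reactions. A safety statement would rest on symptom scores, function tests and whatever participants volunteer.

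The contact imbalance, about 8 against 2 up to month 3, rests on reading bi-weekly as every two weeks. Its effect on reporting cannot be fixed from the documents. It is about 1.2- to 2.0-fold if calls and visits are equally likely (10-50%) to bring out a harm, and close to 1 if calls rarely do. The direction, more detection in NEAT!2+Calls, is plausible but not established.

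The 4.9% bound assumes equal allocation and complete collection in both app arms. Even a well-collected absence of events would be weak evidence of safety at this size. Skin irritation comes from the activPAL, which every arm wears, and says little about the intervention itself.

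**What to change.** Add one row to Table 1, 'Adverse events', at 1, 3 and 6 months. Use the same short REDCap checklist in all three arms, covering the time since the last visit: fall, new knee injury, care sought for the knee, skin reaction.

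In the Statistical Analysis paragraph, state that:
- between-arm harm comparisons use this checklist only, for months 0-3;
- harms first mentioned on coaching calls are listed separately;
- months 3-6 are reported descriptively by actual app use in every arm, because use is then optional;
- skin reactions are reported as a risk of the activPAL, not of the intervention.

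If this is not done, delete 'safe' from E.6 and make no safety claim. The title page notes that the study was stopped, so for data already collected without such a checklist the restriction on claims is what applies.

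The cost is a few items in a survey already given at these visits, and one table. The downside is slight participant burden and a reported harm count above zero.
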